All participants will return after the washout period. Participants in the skin care regimen group will receive Vaseline[®] Moisturizer, Dove[®] Soap, and application log. These participants will be asked to apply the Vaseline[®] Moisturizer twice a day and use Dove[®] Soap daily for 2 weeks. All applications should be reported in the application log by the participants. A demonstration and verbal instructions for how and where to apply the products will be provided to the subjects along with the application log for daily use. Individuals not in the skin care regimen group will continue with the provided Dove[®] Soap.

During this visit, investigators will perform clinical assessments, take photographs and administer subject questionnaires.

Visit 3 (day 14±2):

During this visit, investigators will perform clinical assessment, take photographs and administer subject questionnaires. Application logs will be returned.

Clinical assessment: Clinical assessments will be performed 1) to record baseline skin findings, 2) to evaluate skin status by visual scoring, and 3) to identify any occurrence of any adverse events.

Photography: Standardized digital photographs will be obtained by study staff using a digital camera and software under standard photographic conditions. Photograph files will be coded to remove personal identifiers and stored on a secure hard drive in CTReP.

- b. Study duration and number of study visits required of research participants.
The study consists of up to 3 on-site visits within 4 weeks. We will allow 1 year to complete the study.
- c. Blinding, including justification for blinding or not blinding the trial, if applicable.
NOT APPLICABLE
- d. Justification of why participants will not receive routine care or will have current therapy stopped.
NOT APPLICABLE
- e. Justification for inclusion of a placebo or non-treatment group.
NOT APPLICABLE
- f. Definition of treatment failure or participant removal criteria.

Any clinical findings determined by the Investigator to be important and/or unusual will be referred to as an adverse event (AE). Study participants will be asked to contact clinic staff immediately if they experience an adverse reaction to the products at any time during the study.

Date: 04/05/2018

Principal Investigator: [name], MD

Application Number: IRB00165140

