Such reactions may be documented in a problem events log. The Investigator will use her discretion to remove participants from the study, and all problem events will be reported to IRB.

- g. Description of what happens to participants receiving therapy when study ends or if a participant's participation in the study ends prematurely.
NOT APPLICABLE

5. Inclusion/Exclusion Criteria

Inclusion:

1. Participants must be over the age of 18 years old with dry, itchy skin;
2. Participant must be willing to comply with the requirements of the protocol;
3. Participant must have the ability to understand and communicate with the investigator;
4. Participant must provide informed consent.

Exclusion:

1. Subjects who are unable to provide informed consent;
2. Subjects who are unable to refrain from swimming or hot tub use or no more than 2 showers per day throughout the study duration
3. Subject with significant medical history or current skin diseases that the investigator feels is not safe for study participation;
4. Subjects who have been treated with systemic retinoids or steroids within the past month prior to entry to the study;
5. Subjects who have been treated with topical steroids, retinoids or other topical drugs within 2 weeks prior to entry to the study;
6. Recently treated or current skin diseases that would affect clinical evaluation;
7. Subjects who self-report that they are pregnant or nursing;
8. Patients with history of investigational drug use in the 30 days prior to entry into the study.

6. Drugs/ Substances/ Devices

- a. The rationale for choosing the drug and dose or for choosing the device to be used.

NOT APPLICABLE

- b. Justification and safety information if FDA approved drugs will be administered for non-FDA approved indications or if doses or routes of administration or participant populations are changed.

NOT APPLICABLE

Date: 04/05/2018

Principal Investigator: [name], MD

Application Number: IRB00165140

- c. Justification and safety information if non-FDA approved drugs without an IND will be administered

NOT APPLICABLE

7. Study Statistics

- a. Primary outcome variable.
Clinical/visual scores and subjective score from subject questionnaires.
- b. Secondary outcome variables.
Adverse effects reported by participants and investigator.
- c. Statistical plan including sample size justification and interim data analysis.

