Analysis will include paired and unpaired t-tests with two-tailed p-values. Values obtained at baseline, in middle of the study and after completing the study will be compared. The difference of measure values will be compared between application group and control group.
- d. Early stopping rules.
If the participant wishes to withdraw from the study for any reason, or if the primary caretaker or study investigators wish to cease use of the products.

8. Risks

The moisturizing lotion and wash are generally very well tolerated. Rarely, they can induce a burning sensation, dryness, skin irritation, erythema, stinging, sensitization, and dermatitis. Possible side effects from the product applications include irritant and allergic reactions. Irritation from these agents can be improved or relieved when participants stop using the products. Risk events, problems, and deviations will be reported by the PI directly to the IRB.

In terms of confidentiality, there are minimal risks as all study participant information will be de-identified. No confidential or protected information would be taken beyond the standard. There is a slight financial risk to the participants in the rare event that the above complications occur, requiring additional medical care.

9. Benefits

Date: 04/05/2018

Principal Investigator: [name], MD

Application Number: IRB00165140

Patients with dry skin in the skin care regimen group may experience improvement in their overall skin health. There will be no direct benefit to the participants in the control group. In addition, there is also the potential benefit to society at large. We hope to assess the role of a routine skin care regimen in improving dry skin and reducing symptoms. This can improve quality of life for patients who suffer from dry skin.

10. Payment and Remuneration

Study participants who undergo all study procedures, including correct application of moisturizing lotion and wash in the skin care regimen group will receive a total of \$60 at completion of the study.

11. Costs

Study costs will be covered by the UniLever Corp.

12. References

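### Section 10 makes correct use of the products a condition of the regimen group's $60, with no visible exception for a participant who stops or is removed after a reaction

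*Combined protocol and SAP*

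**What the plan says.** **Payment (section 10).** A single $60 is paid at completion to "Study participants who undergo all study procedures, including correct application of moisturizing lotion and wash in the skin care regimen group". No partial payment is described.

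**Instructed use (section 4a, Visit 2).** The regimen group uses moisturizer twice a day and soap daily for two weeks. "A demonstration and verbal instructions for how and where to apply the products will be provided to the subjects". Controls continue with the soap alone.

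**Reactions (sections 4f and 8).** Section 4f asks participants to contact staff immediately if they react to the products, and says that the investigator "will use her discretion to remove participants from the study, and all problem events will be reported to IRB". Section 8 describes reactions as rare, says that irritation can ease once the products are stopped, and notes a slight financial risk if a complication needs further care. It adds: "Risk events, problems, and deviations will be reported by the PI directly to the IRB".

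**Early stopping (section 7d).** The rule lists a participant's wish to withdraw for any reason, "or if the primary caretaker or study investigators wish to cease use of the products".

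**Outcomes (sections 7a to 7c).** The secondary outcome is adverse effects reported by participants and by the investigator. The primary scores are compared by t-tests that use end-of-study values, which come from Visit 3.

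**The concern.** A participant who develops irritation is told two things that pull against each other. Sections 4f and 8 point towards telling the staff and recognise that stopping the products may help. Section 10, on its face, withholds the $60 from a regimen participant who has not applied the products correctly. It also withholds it from anyone, in either arm, who has not undergone all procedures, and that would include a person removed under 4f after an honest report.

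The practical stake is the adverse-effect outcome, part of which depends on what participants choose to disclose. The explicit condition names only the regimen group, so any reluctance to report could differ between arms. There is also a fairness issue: read literally, someone who reacts could bear the cost of extra care mentioned in section 8 and lose the payment as well.

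A second, separate gap concerns section 7d. It lists ceasing product beside withdrawal from the study and does not say whether Visit 3 still takes place for a participant whose product has been stopped.

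**Working it through.** There is no stated figure to reproduce: the protocol gives no reaction rate, dropout rate, alpha, effect size or standard deviation. The check is mainly a reading of the passages together.

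**1. Who faces the condition.** Section 4a gives up to 100 participants, about 75% regimen and 25% control.
- Regimen: 0.75 × 100 = 75. Control: 0.25 × 100 = 25.
- Section 10's correct-application wording applies to the 75. The requirement to undergo all procedures applies to all 100.

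**2. Is there an exception?** Sections 4f, 4g, 7d, 8 and 10 were read for any statement that payment survives stopping or removal because of a reaction. None is there.

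**3. Do the passages conflict?**
- A regimen participant reacts, reports it and stops: consistent with 4f and 8, but payment under section 10 is in doubt.
- A participant in either arm reacts, reports it and is removed: consistent with 4f, but that person has not undergone all procedures, so section 10 does not pay.
- A regimen participant reacts, says nothing and carries on: contrary to the request in 4f, but section 10 pays.

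Only the third course makes payment certain. That is the conflict.

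**4. What limits the effect.** Adverse effects are also recorded by the investigator. Clinical assessments are intended in part "to identify any occurrence of any adverse events", and at Visit 3 investigators "perform clinical assessment, take photographs and administer subject questionnaires". These checks catch what is visible or disclosed on the day. A reaction that has settled, or a symptom such as stinging, still depends on the participant's account.

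**5. Section 7d and Visit 3, on assumptions only.** Suppose, although the protocol does not say so, that a share p of the regimen arm stopped product and was not seen at Visit 3, and that their outcomes were g SD worse than those of the regimen participants who were seen. With no true effect and completers only:
- Bias b = p × g, in favour of the regimen.
- SE = √(1/25 + 1/(75(1 − p))), in SD units.
- Two-sided error at an assumed alpha of 0.05 = Φ(b/SE − 1.96) + Φ(−b/SE − 1.96).

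| p | g | b (SD) | Type I error |
|---|---|---|---|
| 5% | 0.5 | 0.025 | 0.051 |
| 5% | 1.0 | 0.05 | 0.055 |
| 10% | 0.5 | 0.05 | 0.055 |
| 10% | 1.0 | 0.10 | 0.071 |
| 20% | 0.5 | 0.10 | 0.070 |
| 20% | 1.0 | 0.20 | 0.134 |

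For example, with p = 10% and g = 1: SE = √(0.04 + 1/67.5) = 0.234 and b/SE = 0.427, which gives 0.071. If reactions are rare, the top rows are the more relevant ones. The table shows only what such a loss would do; it is not evidence that any loss will occur.

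**The case against.** The case for leaving the text alone is substantial, and much of it stands.

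- **Consent pages.** Payment terms, including payment after early stopping, may be set out there. This stands, so the finding is limited to the visible text.
- **Meaning of correct.** Given the demonstration at Visit 2, the word may mean only application as shown. That is a natural reading, and on it a person who applied the products properly until a reaction might be paid. But the text does not say so, and it does not help someone removed under 4f.
- **Small sum, rare reactions, other safeguards.** All true. They keep the point minor, but none supplies the missing exception.

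A reader might also infer more than the documents support:

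- **That the application log decides payment.** Section 10 does not mention the log, and no passage links the two.
- **That those who stop product will miss Visit 3.** Section 7d joins withdrawal and ceasing product with an or. It does not cancel Visit 3, and the ceasing it mentions is by the caretaker or investigators. Loss is an inferred risk.
- **That section 4g confirms such loss.** Its heading asks what happens to participants receiving therapy when the study ends or their "participation in the study ends prematurely". The answer is that this is not applicable. Someone who stops product but stays in the study is not clearly within that heading, so it is weak support.
- **That the adverse-effect results will be biased.** Nothing shows this. Payment at completion may even help attendance.

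**Conclusion.** The point holds as a minor one. Section 10 as worded conflicts with sections 4f and 8, and no visible text resolves the conflict for a participant who stops or is removed because of a reaction. About 75 of up to 100 participants face the explicit condition, with $60 at stake for each. The incentive is plainest in the regimen arm but not exclusive to it, because both arms must undergo all procedures and controls also use the soap.

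The effect on reported adverse effects cannot be sized or signed from the documents. The conclusion rests on a literal reading of section 10, which may not be the intended one, and on the consent form not saying otherwise. The silence of section 7d about Visit 3 is a separate gap in wording, and its consequence is a possibility only.

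**What to change.** **Section 10.** Delete the correct-application clause. In substance: participants in both groups receive $60 at completion for attending the study visits and returning any log issued to them, whatever their product use; reporting a reaction, stopping product, or being removed by the investigator because of a reaction does not forfeit the payment. The last provision is needed because a removed participant could not otherwise meet an attendance condition. Align the consent form if it repeats the present wording.

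**Section 7d, reconciled with 4f.** State that ceasing product is not in itself leaving the study, that Visit 3 data are still sought, and that participants are analysed in their assigned group. This concerns data collection and analysis only; no rule on when product should be stopped is proposed.

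**Cost.** A short amendment. The incentive to apply the product is slightly weaker, and the extra outlay is at most $60 for each affected participant. Total payments cannot exceed 100 × $60 = $6,000, which is already the outlay if everyone qualifies. Keeping the payment at completion preserves the reason to attend Visit 3.
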